6.3. Randomisation

Randomisation will be provided by a secure online randomisation system at the Birmingham Clinical Trials Unit (BCTU) (available at www.bctu-redcap.bham.ac.uk/SEEU). Unique log-in usernames and passwords will be provided to those who wish to use the online system and who have been delegated the role of randomising participants into the study as detailed on the SEE U Trial Signature and Delegation Log. The online randomisation system will be available 24 hours a day, 7 days a week, apart from short periods of scheduled maintenance. A telephone toll-free randomisation service ([name]) is available Monday to Friday, 09:00 to 17:00 UK time, except for bank holidays and University of Birmingham closed days.

After participant eligibility has been confirmed by a research nurse or doctor and informed consent has been received, the participant can be randomised into the trial. Paper based randomisation notepads will be provided to investigators and may be used to collate the necessary information prior to randomisation. All questions and data items on the

Randomisation Notepad must be answered before a Trial Number can be given. If data items are missing, randomisation will be halted, and the randomisation process restarted in the trial database once the information is available. Only when all eligibility criteria have been provided will a Trial Number be allocated.

Participants will be randomised at the level of the individual in a 1:1 ratio to either surgical evacuation of products of conception with intraoperative ultrasonography or surgical evacuation of products of conception without intraoperative ultrasonography.

Random permuted blocks of variable length will be used to ensure that the staff recruiting participants to the trial cannot reliably predict the next allocation. To ensure balance in the treatment allocation, randomisation will be stratified by the following variables:

- Proposed anaesthesia type (none/local or general);
- Randomising site

Full details of the randomisation specification will be stored in a confidential document at BCTU.

Following randomisation, a confirmatory e-mail will be sent to the randomising clinician, local PI, local Research Nurse and trial co-ordinating office.

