8.4.5. Post-operative complications

With the exception of intrauterine adhesions, these will need to have occurred within two weeks of treatment and are assessed 2-4 weeks following the procedure. Post-operative complications are defined as any of the following:

- Infection, with a definition based on CDC criteria and other studies as **two** or more of the following (without any **other** obvious cause of infection on history and examination): (1) uterine tenderness, (2) offensive vaginal discharge, (3) high temperature (4) white blood cell count > 12×10^9 /L. To assess this, the patient will be contacted and asked whether they have suffered from: (1) pelvic pain beyond two days of the surgery, (2) offensive vaginal discharge, (3) fever or chills. If they report two or more of these patient-related symptoms then they will be invited in for clinical assessment in line with good clinical practice
- Haemorrhage requiring blood transfusion
- Disseminated intravascular coagulation
- Unplanned hospital admission due to a post-operative complication
- Intrauterine adhesions (defined as the formation of any filmy adhesions) identified at 4-8 weeks following the procedure with hysteroscopy. Pictures of the uterine cavity will be taken and passed on to hysteroscopists blinded to the randomisation. There will be up to five hysteroscopists who will make a majority decision on the presence of the intrauterine adhesions.
- Death

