8.4.6. Unsuccessful procedure

Failed treatment is defined as any of the following:

IRAS ID: 253447

- Failure to completely remove the products of conception during the initial evacuation.
- Positive pregnancy test three weeks after the procedure.
- Repeat surgical evacuation procedure(s) are required before telephone follow-up 2-4 weeks following the procedure.

• Medical management of miscarriage is required before telephone follow-up 2-4 weeks following the procedure.

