8.5. Schedule of Assessments

Visit	Screening (Randomisation, surgery treatment forms)	Visit for surgery (Two week follow-up form)	2-4 weeks post- operative	4-8 weeks post- operative (Hysteroscopy treatment form)
Eligibility check	X			
Relevant medical history taken	x			
Concomitant medication	x	x	x	x
Valid informed consent		x		
Randomisation		X		
Surgical management of miscarriage		x		
Adverse events	x	x	x	x
Collection of outcome data		x		x
Telephone/ In person follow-up			x	
Follow-up office hysteroscopy				x
Site staff interview				x

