13. STATISTICAL CONSIDERATIONS

13.1. Sample Size

The estimated sample size for the substantive study will be partially informed by the output from this pilot study but will be sufficiently powered to detect a minimally important reduction in rates of the composite measure. This study will aim to enroll 90 women. This number will allow us to measure the recruitment rate with 95% confidence interval (CI) width of approximately 10% if we assume 270 will be eligible over six months recruitment and we recruit a third of these.

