13.2. Statistical Analysis

The study size is too small to allow reliable analysis of the effect of the intraoperative ultrasound on outcomes. Analyses of feasibility and clinical outcomes will primarily take the form of simple descriptive statistics (e.g. proportions & interquartile ranges, means and standard deviations) and where appropriate, point estimates of effects sizes (e.g. mean differences and relative risks) and associated 95% confidence intervals. In the first instance, for clinical outcomes, participants will be kept in the groups they were allocated, regardless of compliance with treatment (intention-to-treat). A Statistical Analysis Plan will be generated for review by the Trial Oversight Committee before any analysis takes place.

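### Two parts of the composite's unsuccessful-procedure component do not fit the 2-4 week contact: the repeat-treatment window closes on the call date, and the three-week pregnancy test has no stated collection route

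*Protocol*

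**What the plan says.** Section 8.4.1 makes an unsuccessful procedure one component of the primary composite, and Section 8.4.6 defines it by four criteria. Three of these carry a time:

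- Repeat surgery: "Repeat surgical evacuation procedure(s) are required before telephone follow-up 2-4 weeks following the procedure".
- Medical management: the same cut-off in parallel wording.
- Pregnancy test: "Positive pregnancy test three weeks after the procedure".

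The follow-up meant to supply these data is described elsewhere:

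- Section 8.1 gives the 2-4 week contact one purpose, asking about infection, and says the 4-8 week hysteroscopy is done only to look for adhesions.
- Section 8.5 has no row for a pregnancy test. As the table reads, the row "Collection of outcome data" is ticked at the surgery visit and at 4-8 weeks, but not at 2-4 weeks.
- Sections 9.2 and 9.4 have selected adverse events recorded up to 6 weeks. Repeat evacuation and pelvic infection are on that list; the pregnancy test and medical management are not.
- Section 8.4.5 says of post-operative complications other than adhesions that "these will need to have occurred within two weeks of treatment and are assessed 2-4 weeks following the procedure".
- Section 13.3 proposes no imputation.

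**The concern.** An event definition should give every woman the same period in which to have the event. Here the period for repeat treatment ends on an administrative date, so two women with the same course can be classified differently in the primary composite. The pregnancy test has the opposite problem. Its time point is fixed, but the contact nearest to it may come first, and nothing says who obtains the result or when. A result that is not collected stays missing.

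The stake is the information carried forward. Section 2.1 wants clinical outcome data to inform the next trial's sample size and makes the adequacy of the outcome tools an objective. Section 13.1 says the substantive trial will be powered on the composite. An analysis plan can tidy a definition afterwards, but it cannot recover event dates or test results that the forms never asked for.

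**Working it through.** **Inputs.** Contact window: 2-4 weeks, taken as days 14 to 28 (Sections 8.1, 8.4.6). Test time point: three weeks, taken as day 21 (8.4.6). Risk of repeat surgery: 5 in 100 (3.4, no time horizon given). Planned size: "This study will aim to enroll 90 women" (13.1). Expected follow-up: at least 80% (8.2). Adverse-event period: 6 weeks, or 42 days (9.4).

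**1. The plan's own figure.** The size is meant to "measure the recruitment rate with 95% confidence interval (CI) width of approximately 10% if we assume 270 will be eligible over six months recruitment", with a third of them recruited.

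- 270 / 3 = 90, which reproduces the planned number.
- Wald width: 2 × 1.96 × √[(1/3)(2/3)/270] = 11.2 percentage points. Wilson also gives 11.2, Clopper-Pearson 11.6. This agrees with the stated width only loosely.
- No composite rate enters this calculation, so the size of 90 does not depend on the windows examined here.

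**2. Repeat treatment.** Time at risk is surgery to call: 14 days at the shortest and 28 at the longest, a twofold range. This follows from the definition and needs no assumption.

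To size it, assume that the 5% is the risk over 42 days, and try three timings. Share counted at call day t: t/42 if events are even over time; (1 − 2^(−t/m)) / (1 − 2^(−42/m)) if exponential with median m before truncation at 42 days. Rate counted = 5% × share. Events in 90 women = 4.5 × share.

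| Timing assumed | All called day 14 | All called day 28 | Difference in events |
|---|---|---|---|
| Even over 42 days | 33%, 1.7%, 1.5 events | 67%, 3.3%, 3.0 events | 1.5 |
| Exponential, m = 7 | 76%, 3.8%, 3.4 events | 95%, 4.8%, 4.3 events | 0.9 |
| Exponential, m = 21 | 49%, 2.5%, 2.2 events | 80%, 4.0%, 3.6 events | 1.4 |

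The counted rate therefore runs from 1.7-3.8% to 3.3-4.8% between the extremes of call timing. Medical management has no background rate in the protocol and is not sized.

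**3. Pregnancy test.** Days 14 to 28 are 15 days, of which 14 to 20 (7 days) come before day 21.

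- Calls uniform over the window (assumption): 7/15 = 47%, and 90 × 7/15 = 42 women called before the test. With 80% followed up (72 women), 72 × 7/15 = 33.6, about 34.
- If 25% to 75% of calls were early: 22.5 to 67.5, about 23 to 68 of 90.

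These are women whose call precedes the test, not women whose result is lost.

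**4. Infection, for comparison.** The two-week occurrence window has closed by the time of every contact and is the same for all women. The call date does not change it. What is unclear is how a sign present in the first two weeks is confirmed at an examination prompted by a later call.

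**The case against.** The strongest reply is that the 2-4 week call is not the only source of data. All women are due a 4-8 week visit, where the schedule ticks outcome data and adverse events and where patient feedback is also taken (8.3.1). The description of the hysteroscopy as being for adhesions only explains why it is done; it does not bar other questions. Adverse events run to 6 weeks, Section 7.4 sends procedures and subsequent outcomes from the notes to the case report forms, and Section 8.4.2 lists additional surgery and medical management as secondary outcomes with no call-based cut-off. All of this stands. A reader might infer that 42 test results will be lost, or that treatment after the call goes unrecorded; the documents support neither. They do leave the test without a stated route, and they do exclude later treatment from the composite by definition.

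Three other inferences also go too far:

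- That infection counts depend on the call date. The window is fixed. Leaving out onset after two weeks is a stated definition, and under-counting is plausible but not shown.
- That the missing tick at 2-4 weeks proves outcomes are not collected there. The form labels in the table look shifted by a column (the two-week follow-up form sits under the surgery visit), and Section 8.4.5 places assessment at 2-4 weeks. At most this is clerical.
- That call timing will differ by arm. The trial is open, so it could, but the protocol gives no sign of it.

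It is also fair that the stakes are limited. Of the effect of ultrasound on outcomes, Section 13.2 says "The study size is too small to allow reliable analysis of the effect of the intraoperative ultrasound on outcomes". The later sample size is only partly informed by this pilot, and Section 2.1 singles out adhesions for that purpose.

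**Conclusion.** The point holds for two items in Section 8.4.6. The repeat-treatment window varies from 14 to 28 days with the call date; that is certain from the text. The three-week test can fall after the call and has no schedule row or stated collection route; that is also on the page, while the 47% rests on uniform call dates. The composite rate may be under-counted and partly driven by call date.

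For repeat surgery the size is modest: 0.9 to 1.5 events in 90 women between the extremes, assuming a 5% risk over six weeks and the timings shown. How many test results would go missing cannot be derived from the protocol. The planned 90 and its basis are untouched. For infection, only a clarification is needed.

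**What to change.** - **Section 8.4.6, repeat surgery and medical management.** Replace the cut-off at the call with one fixed counting window from surgery for all women, for example to day 28. Record event dates, and complete them from the notes and at the existing 4-8 week visit. The later source is needed because a call on day 14 or day 21 cannot observe events up to day 28.
- **Section 8.4.6, pregnancy test.** State that the three-week result is collected at a contact on or after day 21, or at the 4-8 week visit.
- **Section 8.5.** Add a pregnancy-test row, and tick outcome data at the 2-4 week contact.
- **Section 8.4.5, infection.** Reconcile occurrence within two weeks with assessment at 2-4 weeks by stating that criteria documented at any earlier attendance count. Leave the definition itself as it is.

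The cost is a wording change, slightly more form completion and slightly longer recall, with no extra visit. Women who miss the 4-8 week visit would rely on the notes; at the expected minimum of 80% follow-up that is up to 90 × 0.20 = 18 women.

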8.5. Schedule of Assessments

Visit	Screening (Randomisation, surgery treatment forms)	Visit for surgery (Two week follow-up form)	2-4 weeks post- operative	4-8 weeks post- operative (Hysteroscopy treatment form)
Eligibility check	X			
Relevant medical history taken	x			
Concomitant medication	x	x	x	x
Valid informed consent		x		
Randomisation		X		
Surgical management of miscarriage		x		
Adverse events	x	x	x	x
Collection of outcome data		x		x
Telephone/ In person follow-up			x	
Follow-up office hysteroscopy				x
Site staff interview				x

8.6. Participant Withdrawal

A participant may be withdrawn from trial intervention if it becomes medically necessary in the opinion of the investigator(s) or clinician(s) providing patient care. In the event of such premature treatment cessation, SEE U study personnel will make every effort to obtain and record information about the reasons for discontinuation and any adverse events, and to follow up all safety and efficacy outcomes as appropriate.

Informed consent is defined as the process of learning the key facts about a clinical trial before deciding whether or not to participate. It is a continuous and dynamic process and participants should be asked about their on-going willingness to continue participation.

Participants should be aware at the beginning that they can freely withdraw (discontinue participation) from the trial (or part of) at any time.

Types of withdrawal as defined are:

- The participant would like to withdraw from trial treatment, but is willing to be followed up in accordance with the schedule of assessments and if applicable using any central UK NHS bodies for long term outcomes (i.e. the participant has agreed that data can be collected and used in the trial analysis).
- The participant would like to withdraw from trial treatment and does not wish to attend trial visits in accordance with the schedule of assessments but is willing to be followed up at standard clinic visits and if applicable using any central UK NHS bodies for post -

operative outcomes (i.e. the participant has agreed that data can be collected at standard clinic visits and used in the trial analysis.)

The participant would like to withdraw from trial treatment and is not willing to be followed up in any way for the purposes of the trial and for no further data to be collected (i.e. only data collected prior to the withdrawal can be used in the trial analysis).

or

On rare occasion, the participant wishes to withdraw completely (i.e. from trial treatment and all follow up) and is not willing to have any of their data, including that already collected, to be used in any future trial analysis.

The details of withdrawal (date, reason and type of withdrawal) should be clearly documented in the source data.

9. ADVERSE EVENT REPORTING

9.1. Reporting Requirements

The collection and reporting of Adverse Events (AEs) will be in accordance with the UK Policy Framework for Health and Social Care Research and the requirements of the Health Research Authority (HRA). Definitions of different types of AEs are listed in the table of abbreviations and definitions. The Investigator should assess the seriousness and causality (relatedness) of all AEs experienced by the trial participant this should be documented in the source data with reference to the protocol.

9.2. Adverse Events (AE)

There are certain AEs which are commonly expected in participants undergoing surgical management of miscarriage. As these events are well characterised, it is highly unlikely that this trial will reveal any new safety information relating to this intervention. The recording of selected AEs will therefore not affect the safety of participants or the aims of the trial.

AE that will be recorded in the Case Report Form (CRF) will include: uterine perforation, cervical trauma, bladder injury, complications of anaesthesia, anaphylaxis, disseminated intravascular coagulation, bleeding (as estimated blood loss in ml and those women requiring blood transfusion), repeat surgical evacuation, pelvic infection, repeat evacuation needed, unplanned hospital admission and intrauterine adhesions (Asherman's syndrome).

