3.4. Assessment of Risk

The safety of the ultrasound is well established. The current consensus is there are no negative side effects to the patient if performing diagnostic ultrasound according to current regulatory guidelines (15).

The risks of the surgical management of miscarriage are outlined within the Royal College of Obstetrics and Gynaecology consent for surgical evacuation of the uterus for early pregnancy loss (16). The serious risks include: uterine perforation (5 in 1000 women) which may require laparoscopy or laparotomy to diagnose or treat organ injury; significant trauma to the cervix (1 in 1,000 to 10,000). Frequent risks include: bleeding that lasts for up to two

weeks is very common but bleeding leading to blood transfusion is uncommon (1-2 in 1,000 women); pelvic infection (3 in 100 women); repeat surgical management (5 in 100 women).

The alternatives include medical management with mifepristone and prostaglandins or expectant management, particularly without an intact gestational sac. These alternatives are associated with heavier and longer bleeding and a 15-50% chance of requiring surgical treatment either as an emergency or the woman's preference.

This trial is categorised as:

Type A: No higher than the risk of standard medical care

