8. OUTCOME MEASURES AND STUDY PROCEDURES

8.1. Clinical assessments and procedures

Procedural and baseline information will be collected prospectively during the intervention. Researchers will input the data directly onto a specifically created case report form. Baseline demographic information will include the patient's age, BMI, gestation, parity, if general anaesthesia is to be used, and type of miscarriage. The type of miscarriage included in this trial will be those diagnosed with early embryonic demise which is a delayed or missed miscarriage: The NICE guidance will be followed for the diagnosis of miscarriage (See box 1).

Following randomisation, the surgical procedure for the management of miscarriage will be conducted with or without intraoperative ultrasonography

Two to four weeks later, patients will be contacted to assess whether they have developed an infection after the procedure.

Four to eight weeks after the procedure, patients will undergo a follow-up hysteroscopy in the office setting without general anaesthesia. This is solely to identify if any intrauterine adhesions have formed following the surgical management of miscarriage. This is an important outcome because the prevalence of intrauterine adhesions is underestimated by clinicians and is thought to be related to the number of curette insertions and how vigorously the curettage in performed [18,19]. Two cohort studies reported 8-19% of women had intrauterine adhesions after surgical management of miscarriage [18,19]. Moreover, intrauterine adhesions can lead to menstrual disorders, infertility, pelvic pain and endometriosis.

Box 1. NICE guidance for diagnosis of non-viable intrauterine pregnancy

1.4.5

When performing an ultrasound scan to determine the viability of an intrauterine pregnancy, first look to identify a fetal heartbeat. If there is no visible heartbeat but there is a visible fetal pole, measure the crown–rump length. Only measure the mean gestational sac diameter if the fetal pole is not visible. 1.4.6

If the crown-rump length is less than 7.0 mm with a transvaginal ultrasound scan and there is no visible heartbeat, perform a second scan a minimum of 7 days after the first before making a diagnosis. Further scans may be needed before a diagnosis can be made.

1.4.7

If the crown-rump length is 7.0 mm or more with a transvaginal ultrasound scan and there is no visible heartbeat:

- seek a second opinion on the viability of the pregnancy and/or

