9.4. Reporting period

The reporting period for AEs is up to 6 weeks post-surgery.

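### Section 9.4 closes adverse event reporting at 6 weeks, but the trial's own hysteroscopy may take place up to week 8 and section 8.5 has adverse events assessed at that visit

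*Protocol*

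**What the plan says.** **The hysteroscopy.** Section 4.1 makes willingness to have it an entry criterion. Section 8.1 places it four to eight weeks after surgery, in the office and without general anaesthesia, and gives its purpose: "This is solely to identify if any intrauterine adhesions have formed following the surgical management of miscarriage". Section 8.4.5 defines adhesions as those "identified at 4-8 weeks following the procedure with hysteroscopy".

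**The reporting period.** Section 9.4 is one sentence: "The reporting period for AEs is up to 6 weeks post-surgery". It does not mention serious adverse events separately.

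**The schedule.** Section 8.5 marks adverse events in all four columns. The last column is the 4-8 week visit, which carries its own "Hysteroscopy treatment form".

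**What is recorded.** Section 9.2 opens: "There are certain AEs which are commonly expected in participants undergoing surgical management of miscarriage". It says these events are well characterised and concludes: "The recording of selected AEs will therefore not affect the safety of participants or the aims of the trial". A list of events for the CRF follows, ending with "unplanned hospital admission and intrauterine adhesions". Section 9.5.1 sends selected events to the CRF. Section 9.1 requires all events to be assessed for seriousness and causality and documented in source data. Section 9.3 collects all serious events.

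**Risk category.** Section 3.4 covers the ultrasound, the evacuation and the alternatives to it, then assigns "Type A: No higher than the risk of standard medical care". It does not mention the hysteroscopy.

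**The concern.** A site needs one unambiguous end date for event reporting, and that date should not fall before a procedure the trial itself requires. Here it can. A site that sees a woman in week 7 and follows 9.4 has no duty to report a non-serious event caused by that hysteroscopy. A site that follows 8.5 would record it. Event counts could then differ between sites because of the rule each followed.

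What is at stake is trial-level information about a procedure done for research. Objective 2.1 asks whether the outcome measurement tools are acceptable and adequate, and the hysteroscopy is the tool for adhesions. How well women tolerate it, and how often it is started but cannot be finished, bear directly on that objective. They also bear on whether a substantive trial could use the same protocol.

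**Working it through.** No sample-size or precision figure in the protocol bears on this point. The check compares two time windows and reads the related sections together.

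**Inputs**
- Hysteroscopy window: weeks 4 to 8, that is days 28 to 56 (4.1, 8.1, 8.4.5).
- End of AE reporting: week 6, that is day 42 (9.4).

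**Share of the window after reporting closes**
- Length of window: 56 − 28 = 28 days.
- Part after closure: 56 − 42 = 14 days.
- Share: 14 / 28 = 0.50, or 50%.

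This is a share of permitted days, not of women. The protocol does not say how visits will be spread. Section 2.1 speaks of adhesions at 6 weeks, which suggests visits may cluster near the boundary. That does not remove the problem, because a hysteroscopy at exactly six weeks leaves no reporting time after it.

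**Can 9.4 and 8.5 be read together?** Take a visit in week 7.
- If the 8.5 mark covers events arising at the visit, 9.4 is wrong, because those events fall after week 6.
- If the 8.5 mark means only asking about events that began by week 6, the sections are compatible. But the hysteroscopy's own events are then excluded.

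Either way 9.4 needs changing.

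**Which events are exposed**

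| Event at a hysteroscopy after week 6 | Position under the protocol |
|---|---|
| Adhesion found | Captured as a primary-outcome component (8.4.1, 8.4.5); the primary analysis waits for this visit (13.5) |
| Serious event | Collected under 9.3, which sets no end date; 9.4 does not say whether its limit applies |
| Non-serious event on the 9.2 list | In source data (9.1); CRF reporting not required under 9.4, implied by 8.5 |
| Non-serious event not on the list | In source data only, whenever it occurs |
| Attempted but not completed | No protocol text requires it; the fields of the hysteroscopy form are not shown |

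**After the change proposed below:** with reporting to at least day 56, 0 of the 28 window days fall after closure.

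**The case against.** The strongest reply is that little is actually lost. Adhesions are captured as an outcome whatever 9.4 says. Serious events are collected under 9.3, and the definition of serious extends to events the investigator considers medically significant. All events and their causality go into source data. The 9.2 list is not tied to one procedure, so uterine perforation, cervical trauma, anaphylaxis, pelvic infection or unplanned admission would be recorded from either procedure. A dedicated hysteroscopy form exists, women give feedback at that appointment (8.3.1), and withdrawal reasons are documented (8.6).

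Most of this stands, and it rules out several stronger readings:
- A reader might infer that adhesions seen after week 6 are lost. They are not.
- A reader might infer that half of the hysteroscopy events will go unrecorded. That would require both an even spread of visits and 9.4 overriding 8.5, and the protocol establishes neither.
- A reader might infer that the hysteroscopy is the sole invasive step the trial adds. Section 7.2 allows the bladder to be filled with saline in the ultrasound arm.
- A reader might infer that the risk category is wrong. Section 3.4 is silent on the hysteroscopy, but silence does not show that another category applies. Section 11.3 also refers to a trial-specific risk assessment that is not shown.

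The reply does not remove the timing conflict. Source notes at sites do not give a trial-level count of non-serious events, and the sections still give different answers about reporting after week 6.

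**Conclusion.** The timing conflict holds on the text and should be corrected. Section 9.4 as written closes AE reporting for half of the permitted hysteroscopy window, while 8.5 marks adverse events at that visit. The consequence is limited to non-serious events at or after later hysteroscopies, plus uncertainty about the period for serious events. It is an ambiguity in the reporting rule, not a demonstrated loss of data. The 50% rests only on the stated windows; a number of women or events would need visit timing and harm rates that the protocol does not give.

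Two secondary points also hold. The argument in 9.2 for selected recording is built on events expected of the evacuation, and the summary in 3.4 covers only the evacuation, its alternatives and the ultrasound. Neither extends to the hysteroscopy. Whether incomplete procedures are already recorded on the hysteroscopy form cannot be settled from the protocol.

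**What to change.** 1. **Section 9.4 (main change).** State that AE and SAE reporting runs to 8 weeks post-surgery or to completion of the hysteroscopy visit, whichever is later. Accept later events by self-report, with no new scheduled contact.
2. **Section 9.2.** Add a line saying how events arising from the hysteroscopy are handled, so that the case for selected recording covers it.
3. **Section 3.4.** Add a line on the risks of the office hysteroscopy as a trial procedure, and confirm or restate the category with it in view.
4. **Hysteroscopy form.** Check its fields. If not already there, add an item for attempted but not completed, with the reason, so that this can be told apart from non-attendance when tool acceptability (2.1) is judged.

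The cost is one revised sentence, two added lines and at most one form item. There are no extra visits or participants, and only slightly more data entry. Self-report after the visit will not capture every late event, but reliable capture would need a further contact for each woman, which this change does not ask for.
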